 - ii) Examining effects of differing doses of anodal tDCS versus sham stimulation on several physiological measures of swallowing, derived from videofluoroscopic swallowing studies;
 - iii) Evaluating durability of any observed effects of tDCS on dietary status as determined by changes in Functional Oral Intake Scale (FOIS) score at study onset and 1 month.
- B) We will assess safety by comparing the anticipated and observed incidence of the following major adverse events in each of the 3 groups: seizures, stroke specific mortality, neurological and swallowing deterioration as measured by changes in NIH Stroke Scale (NIHSS), and FOIS and PAS scores, respectively.

Secondary Aim: To investigate the impact of subject-specific predictors of dysphagia recovery on the outcome of our proposed intervention.

Approach: We will examine differences in the effect size of our intervention across different strata of subject specific-predictors extracted from our pilot model as well as corticobulbar tract (CBT)-lesion load (as a surrogate measure of lesion size and location) by performing a subgroup analysis using regression models.

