b. Neurological and Motor Deterioration: We will only include neurological deterioration not due to a new stroke, hemorrhagic transformation, or a coexisting encephalopathy. Deterioration will be defined as an increase in the NIHSS by ≥ 4 points between each successive day during active or sham stimulation. NIHSS score will be computed at the bedside by an investigator certified in its performance. Similarly motor deterioration for an individual patient is defined as a ≥ 2 point worsening from baseline on the NIHSS motor sub-item score for a given limb.

c. Swallowing Deterioration: We will record a FOIS score on day 3 of our protocol to assess any deterioration of swallowing with the allocated intervention (tDCS or sham). To minimize

radiation exposure VFSS will not be routinely used for this interim assessment. Subject with ≥ 3 point decrease in FOIS, will undergo an interim VFSS to obtain an interim PAS score. Swallowing deterioration will then be defined as an increase in the PAS score ≥ 2 points compared to baseline score based on this interim assessment not due to other confounding factors outlined above.

d. Stroke specific mortality: Deaths due to direct consequences of brain injury such as brain edema or seizure will count for stroke specific mortality, but not deaths from recurrent ischemic events, hemorrhage, pneumonia, cardiac events, and infections. All deaths will be reported to DSMB who will determine if the death is a possible consequence of tDCS or not.

e. Non serious events such as headaches, skin erythema, fatigue and visual perceptual changes will be tabulated to assess patient tolerability but will not be used as primary safety outcome measures due to their subjective nature. The seriousness of any unexpected adverse events such as a serious skin burn will be promptly reported to the DSMB

Secondary Outcomes: We will use 3 outcomes that assess swallowing physiology, 1 outcome that provides functional (dietary) measure of oral intake, and 3 major safety outcomes.

1. Outcomes of Swallowing Physiology:

a) Pharyngeal Constriction Ratio (PCR): PCR is a measure of the pharyngeal area visible in the lateral radiograph view at the point when a bolus is held in the oral cavity divided by the pharyngeal area at the point of maximum pharyngeal constriction during the swallow.

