b) Hyoid, Laryngeal, and Pharyngeal excursion (HLPE): we will measure the actual excursion of these structures and landmarks from their resting point to maximal excursion. Hyoid, laryngeal and pharyngeal excursion are all important and semi-independent movements that close off the airway, shorten the pharynx, and open the upper esophageal sphincter, and thus are important variables to measure.

c) Pharyngeal Delay Time (PDT): will provide a temporal measure of the briskness of the swallow onset. We define PDT as “the time in centiseconds that the bolus is present in the hypopharynx before the swallow is triggered”. PDT will be measured from the time the bolus first passes the intersection of ramus of mandible and base of tongue, until the swallow begins - as seen by the final excursion of the hyoid bone associated with the swallow.

2. Dietary Outcome: Functional Oral Intake Scale [FOIS]: An important consequence of dysphagia is a compromised and altered diet. FOIS is a functional outcome that provides a validated measure of diet level. It has been tested and validated in stroke population and demonstrated to be sensitive to changes in swallowing functions in acute stroke patient. FOIS is an ordinal scale ranging from 1 (worst) to 7 (normal oral diet). It is easy to use and does not require specific training. It will be collected at four time points: 1) prior to initiating tDCS/sham stimulation (same day); 2) after the fifth session of tDCS/sham; 3) after the last session of tDCS/sham stimulation; and 4) by telephone at 1 month after the last stimulation session using a standardized questionnaire.

3.1.3

Protocol for Swallowing Evaluation

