All participants will undergo 3 bedside swallowing evaluation and 2 standardized videofluoroscopic studies (VFSS) to further quantify dysphagia severity. The VFSS will be conducted by the SLPs at BIDMC according to established protocols. The first VFSS evaluation will occur on the day of first tDCS/sham stimulation session and the second evaluation will occur on the last (5th) day of stimulation. Prior to initiation of this project, the participating SLPs at BIDMC will undergo intensive training sessions with [name] (Boston University Medical Center) so that they can reliably detect deep penetration up to the vocal cords or aspiration (PAS score ≥ 4) on VFSS; patients will be enrolled if their PAS score ≥ 4 on at least one swallow. The SLP at BIDMC will not assign PAS scores which will be done by [name] team at their laboratory in Boston University Medical Center (BUMC). The de-identified and coded VFSS will be transferred electronically using a secure file transfer system on the same day to BUMC for detailed analysis and scoring. The lab at Boston University will be alerted immediately and will analyze the studies promptly to assess whether the PAS scores meet criteria for study enrolment. The patient will be viewed in the lateral plane for most swallows, but one swallow will be viewed in the anterior-posterior plane for asymmetry. The order of presentation will not be randomized but given in an incremental way due to the uncertainty about patient's swallowing status and for safety, as outlined below:

In Lateral view: One 5 ml Nectar Varibar Swallow, One 5ml Varibar pudding, 3 Varibar Thin Swallows: 5 ml thin liquids x1, 10 ml thin x 1, 30 ml thin x1;

10 ml & 30 ml thin liquids boluses are given only if no other boluses are aspirated

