A larger area for the reference electrode is chosen to enable current dispersion and minimize any possible biological effect at this site. For sham stimulation, the current will be ramped up to 2 mA and gradually decreased over 30 seconds, to produce a sensation of transient tingling, which is indistinguishable from active stimulation. This device has a “study” mode which allows for double blinding of both the operator and subject. In addition, the SLP involved in bedside swallowing evaluations and VFSS, as well as the investigator performing NIHSS will also remain blinded to the study allocation.

Electrode Placement: *Our aim is to stimulate the inferolateral regions of the primary sensorimotor and premotor cortex of the unaffected hemisphere.* We will use the international 10-20 EEG electrode placement system for this purpose as it has been shown to be accurate and used successfully to identify brain locations in other tDCS studies. We will place the anode mid-distance between C3/T3 [left] or C4/T4 [right] over the unaffected hemisphere and the reference electrode over the contralateral supraorbital region.

- **Stimulation Parameters:** We will use a current dose of 2mA for anodal tDCS. All subjects will undergo daily session of stimulation (tDCS or sham) for 5 consecutive days.

- **tDCS Device Programming and Fidelity Check:** Two individuals (device programmer) not involved in patient recruitment, stimulation sessions or outcome analysis will be assigned to program the tDCS device. They will receive the randomization code from the DCC and set the device to active or sham accordingly. For each treatment they will enter the subject ID and setting on a case report form (‘Blinded Information’ form, for the Data Center only). The programmer will deliver the device to the treating clinician, who after each treatment will return the device to the programmer. The programmer will verify that the device setting is correct and the device is working properly, and enter this information on the case report form.

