 - d. a swallowing deterioration for an individual patient is defined as follows: A FOIS change from baseline of ≥ 3 points will trigger a repeat, interim swallowing assessment; swallowing deterioration will then be defined as an increase in the PAS score ≥ 2 points compared to baseline score based on this interim assessment. The stopping rule for a swallowing deterioration is:
 - i. pause/stop enrollment in a dose if 5/10 or 8/20 in that dose exhibit swallowing deterioration;
 - ii. Pause/stop all enrollment if at least 8/20 or 13/40 patients in both active doses combined swallowing deterioration; note that the probability for these rules is based on the following assumptions and on the binomial distribution:
 1. we assume the natural history of the condition yields probability of swallowing deterioration of 20%;

2. probability of stopping the study for safety, if this is the true probability, using the above stopping rules, is $\leq 5\%$;
 3. thus if the stopping rule is met, odds are that true rates are higher than 20%;
- e. a neurological deterioration for an individual patient is defined as a ≥ 4 point worsening from baseline on the NIHSS global impairment score. The same stopping rule for swallowing deterioration will be applied to neurological deterioration.
 - f. A limb deterioration for an individual patient is defined as a ≥ 2 point worsening from baseline on the NIHSS motor score for a given limb. The same stopping rule for swallowing deterioration will be applied to limb deterioration.

These stopping rules will serve as a guideline, not an absolute end-point, for the DSMB to consider stopping the trial.

All reported AEs and AEs considered by the study investigator to be treatment-related (having a relationship of at least possibly study intervention) will be tabulated for all patients who have received any amount of intervention. Tabulations of serious adverse events will be provided. As part of the AE and serious AE tabulations, the incidence of neurological and swallowing deteriorations will be provided. At regularly scheduled meetings the DSMB will be provided with a copy of all SAE Reports. In addition, the DSMB will be notified of any reportable SAEs as soon as possible in between meetings. Any additional information necessary to evaluate the continued safety of all patients enrolled in this trial will also be provided.

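### Swallowing deterioration is counted only on a FOIS-triggered interim VFSS; a PAS rise of 2 or more first seen on the scheduled Day-5 VFSS is not an event

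*Combined protocol and SAP*

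**What the plan says.** Section 2 makes swallowing deterioration one of the major adverse events of the primary aim. Anticipated and observed incidence are to be compared for "neurological and swallowing deterioration as measured by changes in NIH Stroke Scale (NIHSS), and FOIS and PAS scores, respectively". No time point is attached.

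Section 3.1.2, item c, gives the working definition in three steps:

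- Screen: "We will record a FOIS score on day 3 of our protocol to assess any deterioration of swallowing with the allocated intervention".
- Trigger: "Subject with ≥ 3 point decrease in FOIS, will undergo an interim VFSS to obtain an interim PAS score".
- Event: "defined as an increase in the PAS score ≥ 2 points compared to baseline score based on this interim assessment", with the same exclusions for other causes as neurological deterioration.

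Routine VFSS at this point is avoided to limit radiation.

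Section 6.1.1, item 6(d), repeats the interim-based definition for the stopping rule, with a differently worded trigger and no day: "A FOIS change from baseline of ≥ 3 points will trigger a repeat, interim swallowing assessment". The cut-offs are 5/10 or 8/20 within a dose and 8/20 or 13/40 across both active doses. They are set against an assumed natural-history rate of 20% and a stated false-stop probability of at most 5%. The section calls them a guideline.

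On the scheduled VFSS, section 3.1.3 says "the second evaluation will occur on the last (5th) day of stimulation". PAS is scored by a central laboratory, blinded, as a mean over five swallows. Section 10 lists swallowing deterioration in the adverse event tables up to 30 days after dosing, and in a summary row with seizures, deaths and the other deteriorations. It gives no separate definition.

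**The concern.** The definition rests on an assessment that most patients will not have unless the FOIS screen selects them. It leaves out the one post-baseline VFSS that is planned for everybody. A patient whose average PAS is 2 or more points worse on Day 5, but whose FOIS had not moved by 3 points at the Day-3 check, is recorded as having no swallowing deterioration.

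The stated reason for sparing patients an interim VFSS, radiation, does not apply to a study that is already being done. The neighbouring definition in section 3.1.2 (item b) compares the NIHSS between successive days throughout stimulation, so neurological events are assessed to the end of the treatment week.

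At stake is the observed incidence that the primary aim compares with the anticipated one. As written it is a screened, mid-week count. The 20% reference has no stated definition or window, so the two may not describe the same event.

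**Working it through.** **1. Which patients become events.** Applying the written definition to four patterns:

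| Pattern | Interim VFSS? | Event? |
|---|---|---|
| FOIS down 3 or more at Day 3; interim PAS up 2 or more | Yes | Yes |
| FOIS down less than 3 at Day 3; Day-5 PAS up 2 or more | No | No |
| FOIS down 3 or more at Day 3; interim PAS up less than 2; Day-5 PAS up 2 or more | Yes | No |
| FOIS stable at Day 3, down 3 or more after the last session; Day-5 PAS up 2 or more | No under 3.1.2; unclear under 6.1.1 | No under 3.1.2; unclear under 6.1.1 |

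**2. What lies after the trigger.** FOIS is collected at baseline, "2) after the fifth session of tDCS/sham; 3) after the last session of tDCS/sham stimulation", and at 1 month. The schedule table in section 3.1.4 shows two sessions a day: 2 × 5 = 10. Session 5 is then the first on Day 3, leaving sessions 6–10. If the Day-3 FOIS follows both sessions that day, sessions 7–10 remain. The stimulation text in the same section reads "All subjects will undergo daily session of stimulation (tDCS or sham) for 5 consecutive days", which needs reconciling with the table. With a Day-3 trigger, Days 4–5 are uncovered on any of these readings.

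**3. Scale limits.** FOIS runs from 1 to 7, so a fall of 3 needs a baseline of at least 4 (4 − 3 = 1). Patients starting at 1–3 cannot meet the decrease trigger in section 3.1.2. PAS has a maximum of 8, so a rise of 2 needs a baseline average of 6 or less (6 + 2 = 8).

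**4. The plan's own figure.** Inputs from section 6.1.1: p = 0.20 and the cut-offs. Formula: P(X ≥ r) = Σ from k = r to n of C(n,k) p^k (1 − p)^(n−k).

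- 5/10: 3.28%
- 8/20: 3.21%
- 13/40: 4.32%

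Each cut-off alone meets the stated 5%. Taking both looks of one rule gives 5.2% per dose and 6.1% combined. Any rule in either dose or combined gives 11.7% (simulation, 2,000,000 runs). That is a separate matter, but it shows there is no slack in the bound.

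**5. Hypothetical effect of undercounting.** The documents do not say what share of deteriorations the interim route would catch. The true rates and capture fractions below are all assumptions. The counted rate is true rate × capture.

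| True rate | Cut-off | 100% | 75% | 50% | 25% |
|---|---|---|---|---|---|
| 40% | 13/40 | 87% | 42.3% | 4.3% | 0.01% |
| 40% | 8/20 | 58.4% | 22.8% | 3.2% | 0.04% |
| 30% | 13/40 | 42.3% | 9.6% | 0.4% | <0.01% |

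At 50% capture, a true 40% is counted as 0.40 × 0.50 = 20%, so the chance of reaching 13/40 equals the false-stop figure in step 4.

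**6. The reverse risk.** If the 20% refers to the narrower interim event, and the natural-history rate under a wider definition were 30% (assumption), 13/40 would be reached with probability 42.3% with no treatment harm at all.

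**The case against.** A reader might infer that late worsening never enters the safety assessment. The documents do not support that. Section 2 sets no time limit. Sections 6.1.1, 6.1.2 and 10 give the DSMB PAS change to Day 5 and FOIS change at each visit by group. Section 6.1.2 adds pairwise covariance analyses against sham, and section 9 adds the p-values. Section 6.1.1 also promises by-patient listings, though their PAS content is not specified, and section 9 lets the DSMB ask for more data. Change in mean PAS is the primary efficacy outcome, so a general worsening would show in the main result.

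A reader might also infer that both definitions are tied to Day 3, or that exactly half of the sessions go unassessed. Section 6.1.1 names no day, and the uncovered sessions could be 7–10.

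The Day-3 check can fairly be defended as a mid-treatment safety screen. Swallowing deterioration is absent from the opening list of major safety outcomes in section 3.1.2, and the stopping rules are only guidelines.

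All of this stands, and it narrows the point. It does not close it: group means, ranges and adjusted differences do not give the number of patients worse by 2 points. The section 10 rows either inherit the interim definition or have none. Swallowing deterioration remains in the safety aim and has its own stopping rule.

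**Conclusion.** The point holds as a gap in the event definition. A PAS rise of at least 2 first seen on the Day-5 VFSS is not swallowing deterioration as written. The sections on the aim, the definition, the stopping rule and the tables do not agree on the assessment window. Late harm would be partly visible to the DSMB, but not as a patient count.

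The size cannot be fixed from the documents. The boundary probabilities are illustrations that rest on assumed true rates of 30% and 40% and assumed capture fractions. They also presume that the 20% reference covers all events to Day 5. If it covers only the FOIS-triggered event, count and reference match, and the capture argument against the stopping rule falls away. What then remains is the incomplete incidence reported for the aim. The change is worth making because the data are already being collected.

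**What to change.** 1. In the final safety table and the DSMB table (section 10), add a count by arm of patients whose average PAS on the Day-5 VFSS is at least 2 points above baseline. Apply the same exclusions for other causes and show it separately from interim-triggered events. Give the number with a Day-5 VFSS as the denominator, since section 3.1.6 expects 35–40% attrition.
2. Reconcile sections 2, 3.1.2, 6.1.1 and 10 on the assessment window. Say whether the Day-5 VFSS and the FOIS after the last session count as deterioration assessments, and reconcile the trigger wording (decrease in one place, change in the other).
3. State which event definition and window the 20% reference covers.
4. If Day-5 events are to enter the stopping-rule count, first recheck the 20% rate and the 5% false-stop bound against the wider definition.

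The cost is one table row, a short clarification and a recheck of the reference rate, with no additional VFSS or radiation. If step 4 is taken, the recheck may reach further, because section 6.1.1 applies the same cut-offs to neurological and limb deterioration. The added row does not remove the PAS ceiling: patients with a baseline average above 6 still cannot register a 2-point rise, and a table footnote should say so.

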It has been shown that dysphagia recovery from a hemispheric stroke is associated with an expansion of the swallowing representation in the *unaffected hemisphere*. A treatment approach that facilitates this reorganization in the unaffected hemisphere can help accelerate recovery. Anodal transcranial direct current stimulation (tDCS) is a non-invasive brain stimulation technique that can modulate neuronal excitability of the swallowing motor cortex, and make it more amenable to plastic changes. While it is safe and effective in improving functions in chronic stroke patients, data about its safety and efficacy in acute stroke phase remains sparse. In our pilot study 5 consecutive daily sessions of anodal tDCS to the unaffected swallowing cortex with swallowing exercises was safe and feasible in the acute-subacute stroke phases and showed promise in improving dysphagia. Further confirmation of its safety in early stroke phases and exploration of alternative, more effective doses is vital as a prelude to its examination in confirmatory trials. Besides such **intervention-related factors**, identification of **subject-specific variables** that influence spontaneous swallowing recovery and/or response to the proposed intervention merit examination as they can improve our understanding about the variability of treatment response between subjects, and lead to more efficient study designs by identifying candidates who are more likely to respond to the proposed intervention. We have recently identified a few subject-specific predictors of swallowing recovery from several candidate variables, as outlined in our Preliminary Data. In addition we will use novel neuroimaging measures to obtain surrogate estimates of injury to cortical pathways that regulate

swallowing, and examine the impact of all such subject-related predictors on the effects of our intervention.

Our specific aims are:

Primary Aim: To determine safety and examine effects of 2 different doses of anodal tDCS versus sham stimulation of the swallowing motor cortex of the undamaged hemisphere, combined concomitantly with swallowing exercises, in patients with dysphagia due to an acute-subacute unilateral hemispheric infarction.

Approach:

- A) We will collect data on the effect of our intervention by:
- i) Analyzing changes in penetration and aspiration between the 2 tDCS and sham groups using by a validated assessment tool, the Penetration and Aspiration Scale (PAS) scores;

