Baseline Comparability: While no substantial differences between treatment groups are anticipated given randomization, we will use summary statistics, graphical techniques such as boxplots, and univariate analyses to compare the baseline characteristics of treatment groups. Pre-treatment values will be compared between the placebo- and tDCS-groups using Analysis of CoVariance (ANCOVA) or the Mantel-Haenszel chi-squared test, as appropriate, to determine if the groups are balanced with respect to baseline characteristics while accounting for stratification by dysphagia severity. This comparison will allow us to identify potential confounders to be included in multivariate analyses.

Analytic plan Primary Aim. Primary analysis will use an intent-to-treat approach; thus all randomized subjects will be used in the primary analysis. For the primary outcome variable (PAS) a linear model will be fitted to the data using PROC MIXED in SAS. The outcome will be a change in mean PAS score. Treatment will be included as a categorical variable. Additionally baseline PAS and other variables that will be identified as confounders will be included as covariates. Adjusted means in the two tDCS groups will be compared to those in

the sham group. To control for multiple testing, we will employ the Hochberg-Benjamini procedure, which will result in positive study result if both null hypothesis are rejected at the 0.05 level or one is rejected at the 0.025 level. Similar analyses will be performed on the FOIS, PCR, HLPE, and PDT outcomes. To assess the durability of the intervention effects, a repeated measures analysis will be used. The outcome will be FOIS score at the onset of the trial and at 1 month. Treatment time and their interactions will be included as categorical variables. Additionally other variables that will be identified as confounders will be included as covariates. Adjusted means at the onset of trial and 1 month in the two tDCS groups will be compared to those in the sham group at each time point. *Safety analyses* will be run on all subjects receiving at least one round of intervention. The incidence rates of adverse events will be described as a whole and by treatment group. Adverse events will be presented with and without regard to causality based on the investigator's judgment. *Interim Analyses* No formal efficacy analysis will be performed. The study will not be stopped for early efficacy or futility.

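### Apart from baseline PAS, covariates enter the primary PAS model only through a comparison of the randomized arms, so predictors the team already names enter only if imbalanced by chance

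*Combined protocol and SAP*

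**What the plan says.** Section 3.1.6, Baseline Comparability, opens by expecting little: "While no substantial differences between treatment groups are anticipated given randomization". It then tests baseline values between arms "to determine if the groups are balanced with respect to baseline characteristics while accounting for stratification by dysphagia severity", and states the use of the result: "This comparison will allow us to identify potential confounders to be included in multivariate analyses".

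The primary-aim analysis plan in the same section fits a linear model to change in mean PAS, with treatment as a categorical term. On covariates it says: "Additionally baseline PAS and other variables that will be identified as confounders will be included as covariates". The 1-month FOIS model has the same open wording: "Additionally other variables that will be identified as confounders will be included as covariates". No candidate list, threshold or other selection rule is given.

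Section 2 reports that prognostic information already exists: "We have recently identified a few subject-specific predictors of swallowing recovery from several candidate variables". The secondary-aim plan in 3.1.6 names four predictors: baseline NIHSS, dysarthria, CBT-lesion load and intubation. They are named only there, as main effects and treatment interactions in models for PAS, PCR, PDT and HLPE.

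**The concern.** Adjustment improves precision when a covariate predicts the outcome. A difference between randomized arms carries no information about that. A rule that starts from imbalance will usually leave strong predictors out, and it can bring in variables unrelated to the outcome.

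Two things are at stake. The first is precision in a trial that expects only about 20 completers per arm. The second is prespecification: with neither list nor threshold, nobody can write down the primary model until the arms have been compared. Randomization is stratified on baseline PAS alone, so nothing else in the design brings the named predictors into the primary comparison.

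**Working it through.** **Inputs from section 3.1.6.** 33 randomized per arm; 40% attrition, so 33 × 0.60 = 19.8, taken as 20 per arm (60 in all); type I error 2.5% per comparison; effect 1.0 SD. The study is positive if both p-values are at or below 0.05 or one is at or below 0.025.

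**Assumptions, not in the documents.** Two-sided tests. SD of 1 after baseline PAS. R² is the share of that remaining variance explained jointly, in equal parts, by the three predictors. Prevalence is 50% for dysarthria and 20% for intubation. Selection is by a three-arm F-test adjusted for a split on PAS.

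**Step 1: the plan's own power.** Two-sample t-test, noncentrality d√(n/2), 38 degrees of freedom. At d = 1.0 the noncentrality is √10 = 3.16 and power is 79.3% (stated 80%). At 1.15 it is 89.9% (stated 90%), and at 1.1 it is 86.9% (stated at least 87%). The figures reproduce, and they count on no gain from covariates.

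**Step 2: how often the predictors enter.** Under randomization a balance test at level a admits each predictor with probability a, so none of three independent predictors enters with probability (1−a)³:

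- a = 0.05: 0.95³ = 85.7% (simulated 85.5 to 86.3%)
- a = 0.20: 0.80³ = 51.2% (simulated about 51%)

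**Step 3: approximate break-even.** Three random covariates multiply the variance of the treatment contrast by about (1−R²)(1 + 3/52), where 52 = 60−3−1−3−1. This equals 1 at R² = 0.0577/1.0577 = 0.055. Below that, the fixed list costs precision compared with baseline PAS alone; above it, the list gains.

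**Step 4: power for one active arm against sham** at two-sided 0.025, 20,000 runs per setting (Monte Carlo error about 0.3 points), baseline PAS always in the model:

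| R² | Selected, p<0.05 | Selected, p<0.20 | Fixed list | Fixed minus p<0.05 | SE ratio, fixed / p<0.05 |
|---|---|---|---|---|---|
| 0 | 79.0% | 78.3% | 76.9% | -2.1 | .3266/.3195 = 1.02 |
| 0.05 | 79.0% | 78.4% | 78.9% | -0.1 | .3186/.3194 = 1.00 |
| 0.10 | 79.2% | 79.2% | 81.2% | +2.0 | .3097/.3185 = 0.97 |
| 0.20 | 79.8% | 80.6% | 85.9% | +6.1 | .2921/.3181 = 0.92 |
| 0.30 | 80.1% | 82.0% | 90.6% | +10.5 | .2734/.3173 = 0.86 |

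Against selection at p<0.20 the differences are -1.4, +0.5, +2.0, +5.3 and +8.6 points. Three variants were run at p<0.05: selecting on all 33 per arm; the same with pooled tDCS against sham; and the same with all of R² in NIHSS and prevalences of 70% and 30%. At R² = 0, 0.10, 0.20 and 0.30 they gave -2.1 to -2.2, +1.8 to +1.9, +6.1 to +6.3 and +10.2 to +10.4 points.

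**Step 5: type I error for the whole study**, over the same R² range (Monte Carlo error about 0.15 points):

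- selection at p<0.05: 4.0 to 4.9%
- thresholds 0.05, 0.10 and 0.20 all tried and any positive result kept: 4.7 to 5.2%
- fixed list: 4.4 to 4.8%

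**The case against.** The strongest reply is that the plan delivers what it promises. Its power calculation assumes no covariate gain, and selected-model power in Step 4 is 79.0 to 80.1% at p<0.05, close to the stated 80%. What is forgone is extra precision, and its size depends on an R² that the documents do not give. The predictors concern swallowing recovery in data not shown, whereas the primary outcome is change in PAS over five days. This stands, and it is why the result is a range that includes a small loss.

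The choice of list also matters. The plan names four predictors. With all four, an analytic calculation at R² = 0 gives 76.7% against 80.2% without them, a loss of 3.5 points. Leaving out CBT-lesion load is a judgement, but section 2 supports it. That section sets the load beside the pilot predictors ("different strata of subject specific-predictors extracted from our pilot model as well as corticobulbar tract (CBT)-lesion load") and introduces the imaging measures as new ("In addition we will use novel neuroimaging measures to obtain surrogate estimates of injury to cortical pathways").

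The plan also uses summaries and boxplots, so a p-value filter is only one reading; the 86% and 51% figures illustrate it and are not properties of the plan. A confounder would ordinarily also have to relate to outcome. Imbalance would still be required, so the point survives.

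A reader might infer more than the documents support:

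- *Inflated type I error.* The simulation shows none. It covers three candidates in completers, not an unlimited set of baseline characteristics, nor an analysis of all randomized subjects with imputation, so it does not settle those cases either.
- *An underpowered trial.* The stated power reproduces.
- *Outcome-driven covariate choice.* The comparison uses pre-treatment values only.
- *Predictors ignored.* They are in the secondary-aim models.
- *The same list for FOIS.* The secondary-aim plan does not link these predictors to FOIS, and no calculation was made.

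**Conclusion.** The concern holds as a matter of precision and prespecification. Under the plan's rule, predictors the team already names reach the primary PAS model only through chance imbalance, and the model cannot be stated before the arms are compared.

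A fixed list of three predictors plus baseline PAS changes power from about 2 points worse, if they explain nothing, to about 10 points better at R² = 0.30, with break-even near 0.05. This rests on 20 completers per arm, a 1.0 SD effect, two-sided 2.5%, selection at p<0.05 and an assumed R². It does not call the sample size into question and does not show a false-positive problem. It is a worthwhile, inexpensive improvement, held with medium confidence because R² is unknown.

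**What to change.** Before unblinding, replace the open covariate clause in the primary PAS model with a closed list. Suggested text: *The primary model will contain treatment (three levels), baseline mean PAS, baseline NIHSS, dysarthria and intubation. Baseline comparisons between arms are descriptive and will not change this list. Any model adjusted for an observed imbalance is a sensitivity analysis.*

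- Keep CBT-lesion load in the secondary aim.
- The same three predictors may be used for PCR, HLPE and PDT, with each outcome's own baseline value. The plan already links them to these outcomes, but no calculation was made.
- For the FOIS models, including the 1-month model, require only that the covariates be fixed before unblinding.

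Cost: wording only, since the secondary aim already needs these variables. With 60 completers, residual degrees of freedom fall from 56 (60−3−1) to 53, and about 2 points of power are lost if the predictors explain nothing.
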